Abbreviation	Definition
ACD	All-cause discontinuation
AE	Adverse event
AIMS	Abnormal Involuntary Movement Scale
AL-LAI	Aripiprazole lauroxil, long-acting injectable (ARISTADA®)
AL-NCD	Aripiprazole lauroxil NanoCrystal® Dispersion (ARISTADA INITIO®)
ARI-ORAL	Oral aripiprazole
BARS	Barnes Akathisia Rating Scale
BPRS	Brief psychiatric rating scale
C-SSRS	Columbia suicide severity rating scale
CATIE	Clinical Antipsychotic Trials of Intervention Effectiveness
CGI-S	Clinical global impression – severity
CYP	Cytochrome P450
DSM-5	Diagnostic and Statistical Manual of Mental Disorders, 5th Edition
EPS	Extrapyramidal symptoms
ESRS-A	Extrapyramidal symptom rating scale
FDA	Food and Drug Administration
GASS	Glasgow Antipsychotic Side-effect Scale
GFS	Global functioning scale
GLMM	General linear mixed models
ICF	Informed consent form
IRB	Institutional review board
IM	Intramuscular
ITT	Intent-to-treat
MCCB	Matrics consensus cognitive battery
MSQ	Medication satisfaction questionnaire
NIMH	National Institute of Mental Health
PANSS	Positive and Negative Syndrome Scale
PSP	Personal and Social Performance
QLS	Quality of Life Scale
RAISE	The Recovery After an Initial Schizophrenia Episode (study)
SAE	Serious adverse event

Abbreviation	Definition
SANS	Scale for the Assessment of Negative Symptoms
SCID	Structured Clinical Interview for DSM-5
SES	Service engagement scale
SIStat	Semel institute biostatistics core
SUI-Brief	Brief substance use inventory
SUMD-R	Scale to Assess Unawareness of Mental Disorder-Revised
UCLA	University of California, Los Angeles
WTAR	Wechsler Test of Adult Reading

4. INTRODUCTION

Long-acting injectable antipsychotic medications are a critical tool for clinicians treating schizophrenia patients. There is a growing consensus that long-acting injectable options should not be reserved only for the very ill who have demonstrated nonadherence to oral antipsychotic medication. Additional research into their effectiveness may be required in order to inform physicians of the use long-acting injectable medications early in the course of the disorder. Ensured adherence using long-acting injectables allows the clinician to better judge the effectiveness of the medication and dosage, and guide the pharmacologic treatment early in disease.

Aripiprazole lauroxil, long-acting injectable (AL-LAI; ARISTADA[®]) is an atypical long-acting injectable for the treatment of schizophrenia. It is a covalently bonded, non-ester modification of aripiprazole, a second generation atypical antipsychotic agent, to form *N*-lauroyloxymethyl aripiprazole. It is formulated as an extended-release suspension to be administered via intramuscular (IM) injection into either the gluteal or deltoid muscles. After injection, aripiprazole lauroxil is converted to aripiprazole by dissolution of the aripiprazole lauroxil drug crystal from the injection site and subsequent enzyme-mediated cleavage, ultimately releasing aripiprazole into the plasma circulation.

Therapy may be initiated by a one-day initiation regimen (a single IM injection of 675 mg aripiprazole lauroxil NanoCrystal[®] Dispersion [AL-NCD; ARISTADA INITIO[®]] with a single-dose of 30 mg oral aripiprazole [ARI-ORAL]) or by 21 consecutive days of supplementation with ARI-ORAL. AL-NCD is a different IM formulation of AL. The two IM formulations predominantly differ in the particle size of the drug substance, the AL-LAI in the micrometer range and AL-NCD in the nanometer range. The smaller particle size of the AL-NCD formulation is designed to accelerate the rate of dissolution of AL to provide earlier appearance of circulating aripiprazole following administration compared to the micron formulation.

In clinical trials, treatment with AL-LAI demonstrated statistically significant reductions from baseline in Positive and Negative Syndrome Scale (PANSS) total scores at Week 12, compared with placebo. AL-LAI was generally well tolerated for patients with schizophrenia at monthly IM dosing of 441 mg and 882 mg with the most common adverse events (AEs) being insomnia, akathisia, and headache.

This study is an open label, 12-month prospective evaluation comparing ARI-ORAL to AL-LAI conducted by the University of California, Los Angeles (UCLA).

5. STUDY OBJECTIVES

5.1. Primary Objective

The primary objective is to assess whether schizophrenia patients who recently experienced their first psychotic episode that are randomized to AL-LAI are less likely to experience a re-emergence of positive psychotic symptoms compared to those randomized to ARI-ORAL.

5.2. Secondary Objectives

The secondary objectives are to:

1. Examine differences in functional outcome between the two treatment groups. We anticipate that role functioning will improve more in the group randomized to AL-LAI than those assigned to the ARI-ORAL group.
2. Evaluate and compare the cognitive changes of the AL-LAI vs. ARI-ORAL group over the 12-month Treatment period. It is hypothesized that patients assigned to AL-LAI will demonstrate relatively better performance on a standardized measure of cognition than those assigned to ARI-ORAL.

5.3. Exploratory Objectives

Additional exploratory objectives are to determine whether the two medication groups differ in other symptoms domains, adherence, and tolerability (eg, negative symptoms, suicidality, self-reported awareness of having a mental disorder, service engagement, sexual/ prolactin-related side effects, treatment engagement, and quality of life).

6. SELECTION AND WITHDRAWAL OF PATIENTS

Approximately 128 patients will be recruited for the study as defined by consenting to a full screening assessment with the goal of randomization to a treatment group. Based on prior long-acting injectable versus oral studies, we expect an attrition rate of 30% prior to Randomization, so that a total of 90 eligible patients will be randomized to either ARI ORAL (N=45) or AL-LAI (N=45).

6.1. Inclusion Criteria

Each patient must meet all of the following inclusion criteria to be qualified to participate in this study.

3. Is willing and able to provide informed consent.
4. Is between 18 and 45 years of age, inclusive, at Screening.
5. Has a diagnosis of schizopreniform disorder, schizophrenia, or schizoaffective disorder, depressed type, as defined by Diagnostic and Statistical Manual of Mental Disorders, 5th Edition [DSM-5] ([American Psychiatric Association 2013](#)) criteria at Screening.
6. Has a first episode of a psychotic illness that occurred within the 24 months before entry into the UCLA Aftercare Research Program.
7. Sufficient acculturation and fluency (oral and written) in the English language to avoid invalidating research measures of thought, language, and speech disorder or of verbal abilities.
8. Exhibits tolerability to ARI-ORAL during the Stabilization period, according to Investigator judgment (to be randomized).
9. Resides within commuting distance of the UCLA Aftercare Research Program in a stable living situation where the patient can be located.
10. Agrees to abide by the contraceptive requirements of the protocol.

6.2. Exclusion Criteria

Each patient must not have any of the following conditions to be qualified to participate in this study.

1. Evidence of a known neurological disorder (e.g., epilepsy) or significant head injury with loss of consciousness of more than one hour.
2. Has mental retardation (i.e., premorbid IQ less than 70) as estimated by the Wechsler Test of Adult Reading (WTAR) completed at screening or as documented in medical records conducted in childhood. The WTAR assesses word pronunciation, which is thought to be unaffected by cognitive decline associated with neurological damage and is thus a good proxy for premorbid intelligence.
3. Is currently pregnant or breastfeeding, or is planning to become pregnant during the study.

4. Is currently on a long-acting injectable antipsychotic medication and it is clinically contra-indicated due to the risk of becoming a danger to self or others if the patient discontinued treatment with the long-acting injectable in order to participate in this trial.
5. Has a history of poor or inadequate response to an adequate trial of oral or injectable aripiprazole (does not exclude patients whose aripiprazole exposure was too brief or at sub-therapeutic doses).
6. Has received AL-LAI or IM depot aripiprazole within two months prior to Randomization (unless Stabilization period is extended beyond 90 days to accommodate).
7. Has alcohol or substance abuse as a prominent clinical problem or makes the primary diagnosis not possible to confirm. Evidence of alcohol or substance use is not, in and of itself, exclusionary.
8. Is currently being treated with clozapine.
9. Has participated in a clinical trial involving any drug within the past two months prior to screening, or is currently participating in a clinical trial involving an investigational medication.
10. Has a history of psychopathology based on the screening SCID other than schizophreriform disorder, schizophrenia, or schizoaffective disorder, mainly depressed type as indicated by any primary DSM-5 diagnosis within the 12 months prior to Screening or Randomization (e.g. primary diagnosis of bipolar disorder, schizoaffective disorder, bipolar type, bipolar disorder, or neurocognitive disorder) based on our research diagnostic procedures.
11. Is in the opinion of the Investigator or prescribing psychiatrist, the patient is an imminent danger to himself/herself. Patient must not be an imminent danger to himself/herself for two weeks prior to entry. The Stabilization period may be extended until the potential patient participant has not been in imminent danger to himself/herself for at least two consecutive weeks. A prior history of suicidal ideation or suicidal attempt is not exclusionary.
12. Has any of the following conditions or abnormalities at screening: History of neuroleptic malignant syndrome, malignant hyperthermia, or clinically significant tardive dyskinesia.

6.3. Discontinuation of Assigned Medication

If the randomly assigned medication must be discontinued and/or switched to a different antipsychotic medication, the patient may remain in the study until the 12-month assessment point. End of Assigned Treatment assessment point measures will be completed as close to and if possible, just prior to, the discontinuation/switch. Decision to switch medication will be recorded on a modified Clinical Antipsychotic Trials of Intervention Effectiveness (CATIE) All-Cause Discontinuation (ACD) assessment completed by the treating psychiatrist (Stroup et al, 2003). The switch to another antipsychotic medication will be guided by clinician judgment using the medication selection recommendation adapted from the oral antipsychotic guidance used in the RAISE study (Kane et al, 2015). The date the new medication is prescribed will be recorded and used in the analyses. Patients who choose to discontinue study medication will be allowed to re-

initiate study medication at any time during the 12-month follow-up. All other regular assessments will be completed throughout the remainder of the 12-month study.

6.4. Over-enrollment of Patients

Over-enrollment (beyond 90 patients) will occur to ensure that there are at least 14 patients who had a relapse in the 12-month Treatment period.

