Randomization to ARI-ORAL: Patients will continue with ARI-ORAL doses within the recommended oral dosage range for the treatment of schizophrenia (10-30mg/day) with the usual starting dosage of 10 mg/day. ARI-ORAL dosage will be flexible and dosage will be at the discretion of the treating psychiatrist. Patients assigned to this treatment arm will receive a written prescription for a 30-day supply along with a medication coupon so there will be no medication cost to the patient.

Discontinuation of Assigned Treatment

Both groups will remain on their assigned treatment for 12 months or discontinue their assigned medication early. The reason(s) for early discontinuation of initial antipsychotic will be recorded, including whether it is initiated by the clinician or patient, and whether it is efficacy or tolerability related. Patients will be assessed for the reason for discontinuation using a version of the All-Cause Discontinuation (ACD) measure that was the primary outcome of the CATIE schizophrenia study. If a switch to another antipsychotic medication is warranted, the new therapy will be determined by the prescribing psychiatrist's judgment using the medication selection recommendation adapted from NAVIGATE pharmacologic treatment manual developed as part of the Recovery After an Initial Schizophrenia Episode (RAISE) study intervention groups. Patients discontinuing study drug after Randomization, but remaining in active treatment and follow-up, may be prescribed any first-line oral antipsychotic within the prescribing information dosage for schizophrenia. Patients will be encouraged to stay in the study for the remainder of the 12-month Treatment period and will be administered all of the scheduled assessments even if the initial randomly assigned antipsychotic medication is discontinued by the treating psychiatrist.

Symptom assessments will occur every two weeks, functional endpoint will occur every three months, and the cognitive endpoint will occur at baseline and at the 6- and 12-month points. All patients participating in the protocol will be invited to concurrently participate in a separate NIMH-funded psychosocial intervention protocol comparing the effectiveness of computerized cognitive training with and without aerobic exercise training.

Number of Patients Planned: Approximately 128 patients enrolled into the Stabilization period for final randomized sample of 90 (45 in each group) with a target of 14 relapses

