Criteria for Efficacy Evaluation: Primary Endpoint The primary endpoint will be time to first positive symptom exacerbation and/or relapse following a period of absence or relatively low levels of psychotic symptoms based on the expanded 24-item version Brief Psychiatric Rating Scale. Secondary Endpoints Functional assessment: The Role ratings on the Global Functioning Scale (GFS: Role) will serve as the measure of functional outcome. The GFS: ROLE will be administered every three months throughout the 12-month Treatment period. Cognitive assessment: The Overall Composite T-score from the MATRICS Consensus Cognitive Battery (MCCB) will be the overall index of cognitive performance. The MCCB will be administered every six months throughout the 12-month Treatment period. Exploratory Endpoints Endpoints include Quality of Life, negative symptoms, self-reported awareness of having a mental disorder, service engagement, prolactin-related side effects, treatment satisfaction, and family/caregiver medication administration burden. Safety Assessments Extrapyramidal symptoms will be assessed on three scales (Abnormal Involuntary Movement Scale, Barnes Akathisia Rating Scale, and the Extrapyramidal Symptom Rating Scale). Adverse events (including serious and AEs of special interest), and suicidality will be monitored.
Statistical methods: Sample Size Considerations: Ninety first-episode patients will be randomized (1:1) fashion to either AL-LAI or ARI-ORAL, and based on our previous RCT, assume a 20% attrition rate over 12 months. 45 randomized patients (36 completers) in each group provides at least 80% power. Statistical power considerations are based on the effect sizes observed when comparing long-acting injectable risperidone vs oral risperidone (survival analysis for psychotic relapse: 5% relapse in the risperidone long-acting injectable group and 33% relapse in the oral risperidone group). On the basis of hazard function rates of 5.0% (AL-LAI)

and 33% (ARI-ORAL), the study has 87% power ($\alpha=0.05$). On a more conservative basis of hazard function rates of 7.5% (AL-LAI) and 33% (ARI-ORAL), the study has 78% power ($\alpha=0.05$).

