7. STUDY DESIGN

7.1. Overall Study Design

[figure not shown]
This is an open-label study of approximately 90 patients with schizophrenia who will be randomly assigned to 12 months of treatment with either ARI-ORAL or AL-LAI to take place at the UCLA Aftercare Research Program ([name]), which is a program that specializes in the treatment and study of individuals with a recent onset of schizophrenia. The study design is presented in [Figure 1](#). Potential patients will be evaluated for eligibility according to the inclusion and exclusion criteria at Screening.

For patients who have never taken aripiprazole, tolerability must be established during the Stabilization period. The Stabilization period will be once-a-day ARI-ORAL with flexible dosing. All patients will receive ARI-ORAL for at least two weeks to establish full tolerability before Randomization, and patients who cannot tolerate ARI-ORAL 10 mg/day will not be randomized. Eligibility to be randomized will be determined at the end of the Stabilization period of up to 90 days.

The Stabilization period will allow time for the oral antipsychotic medication to be cross-tapered to ARI-ORAL, if needed, and allow time for the patient to obtain some clinical stability prior to Randomization. Further, the Stabilization period will allow the baseline testing for this and the overlapping National Institute of Medical Health (NIMH) protocol to occur at a pace appropriate for someone who is in the middle, or tail-end of, a psychotic episode.

Randomization (1:1 [AL-LAI: ARI-ORAL]) will take place after the Stabilization period. The NIMH overlapping study is a psychosocial intervention treatment. To balance the overlapping NIMH treatment groups in the AL-LAI and ARI-ORAL treatment groups, the randomization of patients in the APPRIASE study will be stratified by their participating role in the NIMH study (randomized to computerized cognitive training with or without aerobic exercise). Once randomized, patients will be treated per prescribing recommendations for a 12-month Treatment period.

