Efficacy will be evaluated based on the Brief Psychiatric Rating Scale (BPRS) scored for symptom exacerbation or relapse following Subotnik et al. ([Subotnik et al, 2015](#)) and Nuechterlein et al. ([Nuechterlein et al, 2006](#)). Because patients will not be withdrawn from the study if relapse criteria are met, there will be no need to score the BPRS for relapse contemporaneously throughout the study. Secondary outcomes will be role functioning and cognition. Exploratory outcomes will be negative symptoms, suicidality, awareness of having a mental disorder, extrapyramidal and prolactin-related side effects, service engagement, treatment satisfaction, and quality of life. Safety assessments will be collected and monitored.

Figure 1: Study Design

^a 1 to 3 months of stabilization on oral aripiprazole.

^b For 2 weeks prior to Randomization, all patients must be on oral aripiprazole

^c Initiation of treatment per Section 7.2.2

Abbreviations: ARI-ORAL: aripiprazole oral; AL-LAI = aripiprazole lauroxil long-acting injectable; ET = End Treatment; EoS = End of Study

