7.4.6.1. APPRAISE Study Criteria for Reemergence of Positive Symptoms

The BPRS is a semi-structured instrument that is internationally recognized and accepted for rating the presence and severity of psychiatric symptoms. The BPRS assesses various domains of psychiatric symptoms. Ratings are based on information obtained from self-report and observation of the patient's behavior and speech. Symptoms and signs are rated along a severity and impairment in functioning dimension using a seven point rating scale. The BPRS has been used extensively to assess changes over time in the severity of the symptoms of schizophrenia and other major psychiatric disorders. In a comprehensive review, Hedlund and Vieweg ([Hedlund JI 1980](#)) found that most studies reported excellent inter-rater reliability for the BPRS. Median Pearson and Intraclass correlation coefficients on the BPRS have ranged from 0.67 to 0.88 ([Bech et al, 1988](#); [Tarell and Schulz 1988](#)). The UCLA research team has developed a training and quality program for the expanded BPRS that has led to excellent inter-rater reliability at the completion of training ([Ventura et al, 1993](#)). The case managers will complete the BPRS at Screening and every two weeks as identified in [Table 2](#).

The BPRS includes ratings from 1 to 7 on each of these symptom dimensions. However, for positive symptom exacerbation, the three key BPRS ratings for predicting and evaluating psychotic relapse or significant exacerbation are:

1. Hallucinations
2. Unusual Thought Content
3. Conceptual Disorganization

It is these three items that are scored into the relapse algorithm.

Because patients will vary based on their relative stability over time as well as the degree of change in positive symptom severity, the actual relapse outcome will be based on *both* current and prior BPRS evaluations as specified by one of the three exacerbation/relapse categories. Meeting criteria for any of the following three categories will be considered a psychotic relapse/exacerbation.

Criteria for relapse or exacerbation of symptoms are summarized in [Table 3](#). These criteria have established reliability, predictive validity and reactivity to medication nonadherence. Assessments are done every 2 weeks and scoring done by computer program.

Table 3: Criteria for Relapse or Exacerbation of Symptoms

Remission followed by relapse	Remission followed by 1 psychotic item ≥ 6 (severe) at any BPRS assessment visit	Section 7.4.6.1.1

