7.4.6.1.3. Persisting Symptoms Followed by Significant Exacerbation of Symptoms

The patient has persisting clinically significant symptoms in the 4 to 5 range on one or more BPRS key items but not in the 6 or 7 range for more than four weeks (not necessarily always the same item) during the Treatment period without achieving remission (by criteria above), and:

- shows an increase of two points within an eight-week period to a rating of 6 or 7, or
- shows an increase of one point on this item to a 6 and an accompanying two-point increase on another key symptom item within the same four-week period.

These criteria are not made in real time, but are entered into the database and determined at a later time.

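### Does the promise of at least 14 relapses leave the sample size undefined?

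*Combined protocol and SAP*

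**What the plan says.** Section 6.4 is a single sentence: "Over-enrollment (beyond 90 patients) will occur to ensure that there are at least 14 patients who had a relapse in the 12-month Treatment period". The Synopsis states the same intention more softly, as a "final randomized sample of 90 (45 in each group) with a target of 14 relapses".

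The sample size itself is set out in terms of patients. The Synopsis states that "45 randomized patients (36 completers) in each group provides at least 80% power". Section 6 starts from about 128 consenting patients: "we expect an attrition rate of 30% prior to Randomization, so that a total of 90 eligible patients will be randomized". Section 7.1 begins: "This is an open-label study of approximately 90 patients with schizophrenia". The Synopsis estimates the last visit at 48 months after the first consent.

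On timing of the relapse determination, section 7.1 says that "there will be no need to score the BPRS for relapse contemporaneously throughout the study", and section 7.4.6.1.3 adds: "These criteria are not made in real time, but are entered into the database and determined at a later time". Section 7.4.6.1 describes the process: "Assessments are done every 2 weeks and scoring done by computer program". Section 14.1 gives data management and analysis to the biostatistics core, which holds a central database. The monitoring committee in section 7.4.9.1 has a safety remit only.

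**The concern.** Section 6.4 promises a result without the means to deliver or end it. Nothing states who counts relapses, when, whether the arms are pooled, how patients still in follow-up are treated, what the largest sample is, or what happens if 14 is never reached. The planning figures (128, 90, 48 months) are not tied to the rule, and section 6.4 expressly overrides the 90. Because scoring is deferred, the count that would drive over-enrolment is not scheduled to exist while recruitment is open.

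Read literally, one site could be committed to many more patients and months than planned, and an ethics board or drug supplier could not tell from the text how many. Two statistical worries would be more serious: that the stated power depends on reaching 14 events, and that a data-dependent sample size distorts the type I error.

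**Working it through.** **1. What the stated power rests on.** Inputs (section 12.1.1 and Synopsis): relapse 5% or 7.5% against 33%, two-sided alpha 0.05, 45 x 0.80 = 36 completers per group. Two-proportion test with pooled variance under the null:

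z = [|p1 - p2| - 1.96 x sqrt(2 x pbar x (1 - pbar)/n)] / sqrt([p1(1 - p1) + p2(1 - p2)]/n)

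- 5%/33%: pbar = 0.19, z = (0.28 - 0.1812)/0.0864 = 1.14, power 87.4% (stated 87%).
- 7.5%/33%: pbar = 0.2025, z = (0.255 - 0.1857)/0.0898 = 0.77, power 78.0% (stated 78%).

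The stated figures therefore follow from 36 completers per group, and no event count enters them.

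**2. Where 14 may come from.** Expected relapses among 36 completers per group are 36 x (0.05 + 0.33) = 13.7 and 36 x (0.075 + 0.33) = 14.6. The hazard ratio implied by 5% and 33% is ln(0.95)/ln(0.67) = 0.128. Freedman's formula then requires ((1 + 0.128)/(1 - 0.128))^2 x (1.96 + 0.84)^2 = 13.1 events for 80% power, rounded up to 14. The plan does not state the origin, but 14 is a reasonable floor on either basis.

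**3. How often 90 patients fall short of 14.** The total is the sum of two binomials, so the probability is exact once the handling of attrition is chosen. With exponential dropout, the chance of an observed relapse is l/(l + c) x (1 - exp(-(l + c))), where l = -ln(1 - p) and c = -ln(0.8). This gives 0.0449, 0.0673 and 0.2980 for p = 5%, 7.5% and 33%, so 45 per group yield 15.4 or 16.4 expected relapses.

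| Attrition handling | P(<14), 5%/33% | P(<14), 7.5%/33% |
|---|---|---|
| Only the 36 completers per group contribute | 49% | 38% |
| 45 per group, 20% exponential dropout | 29% | 20% |
| All 45 per group fully observed | 15% | 9% |

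**4. What the literal reading does.** The plan gives no accrual rate. Assume 90 randomised evenly over 48 - 15 = 33 months, 20% exponential dropout, recruitment continuing until the 14th relapse has been seen, and no ceiling. By simulation, N exceeds 90 in about 57-61% of trials at 5%/33% and 48-50% at 7.5%/33%; the spread reflects whether the decision falls at the 90th or the 91st entry. Mean N is about 101 and 98. At 30% loss before randomisation, a mean of 101 means 101/0.70 = 144 consenting, against the planned 128.

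**5. Validity.** With no treatment difference (both arms at 19%, then both at 15%), the log-rank type I error under the literal pooled rule is 4.8% and 5.0%.

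**6. What the alternatives would buy.** Log-rank power under the same assumptions; the 5%/25% scenario is an assumption, not a figure from the plan:

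| Rule | 5%/33% | 7.5%/33% | 5%/25% |
|---|---|---|---|
| Extend until 14 relapses, no ceiling | 97% | 90% | 88% |
| Projected count, illustrative ceiling of 100 | 94% | 87% | 79% |
| Fixed at 90 | 93% | 85% | 76% |

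**The case for a change.** The strongest case for a change is that two sentences would settle the matter: a pooled count made by the biostatistics core at set times, observed or projected, with a ceiling and a statement that analysis proceeds if 14 is not reached. Writing this down beforehand would also guard against an improvised decision in an open-label trial. The literal reading can be costly: under the assumed accrual the 95th percentile of N is about 130 at 5%/33% and 123 at 7.5%/33%. Some of that extension is unneeded, because the first 90 would have reached 14 with further follow-up.

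Part of this stands. No procedure or maximum is given, and stating one would be tidy. The size of the burden is less firm. It depends on an accrual rate that the plan does not give and on an immediate count that sections 7.1 and 7.4.6.1.3 do not envisage. Section 6.4 refers to relapses within the 12-month period, which also fits a count after follow-up; extension would then be needed only as often as the table in step 3 shows. Unneeded extension is about half of all extensions at the planning rates but only about 22% at 5%/25%. The calendar limit is also soft: section 7.1 allows 1 to 3 months of stabilisation, so the randomisation window could be 48 - 1 - 12 = 35 months rather than 33.

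Deferred scoring does not contradict section 6.4. The text says that contemporaneous scoring is unnecessary; it does not rule out a periodic run.

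**Conclusion.** The plan leaves out an operating detail, and no change is needed. Its primary comparison is sound whether or not enrolment goes past 90: 45 per group already carries the stated power, extra patients can only add to it, and a pooled count leaves the type I error at 4.8-5.0%. The missing step is one that the analysts can fill sensibly, since the relapse definition is explicit, scoring is automated and the biostatistics core holds the data.

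The parts of a revision that would alter the design, a ceiling or a fixed 90, are a trade-off and not a correction. They limit patients and time but give up protection if oral relapse is lower than planned (power 79% or 76% instead of 88% at the assumed 5%/25%). Reasonable statisticians would differ on that.

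This conclusion assumes that any extension depends on the total number of relapses and not on a comparison between arms. Section 6.4 mentions only a total. The power and sample-size simulations assume constant hazards, 20% exponential dropout and even accrual; the range for the chance of fewer than 14 relapses covers the main ways of treating attrition.
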